### **Background and Rationale**

Attention Deficit and Hyperactivity Disorder (ADHD) is a multifactorial neurodevelopmental disorder characterized by attention deficits, impulsivity, and hyperactivity. This study investigates the effect of music-based occupational therapy on attention and executive functions in children with ADHD. Music-based rhythmic and motor activities are hypothesized to enhance cognitive, emotional, and behavioral regulation.

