### **Objectives**

#### **Primary Objective:**

To examine the effect of music-based occupational therapy on attention performance in children with ADHD.

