#### **Secondary Objective:**

To evaluate the effects of the intervention on executive function skills and caregiver burden.

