## **Intervention**

#### **Experimental Group:**

Music-Based Occupational Therapy - structured rhythmic, singing, and instrument-based (harmonica, drum) sessions designed to improve self-regulation and executive functions.

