## **Outcome Measures**

#### **Primary Outcome:**

- Change in attention (DSM-V Level 2 Inattention Scale)

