#### **Secondary Outcomes:**

- Executive Function (Childhood Executive Function Inventory)
- Caregiver Burden (Zarit Burden Scale)

All measures assessed pre- and post-intervention.

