## **Data Analysis Plan**

The analyses were performed using SPSS 25.0 software. For descriptive statistics, mean, standard deviation, and percentage values were used. Normal distribution was checked with the Kolmogorov-Smirnov Test. For independent variables, nominal data were evaluated with the Chi-Square Test, while numerical data were assessed with the T-Test / Mann-Whitney U Test. Two-Way Repeated Measures ANOVA was applied for within-group and between-group time interactions. The significance level for all tests was accepted as  $p < 0.05$ .

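### Does one 0.05 threshold for all tests leave it unclear whether executive function could carry the trial?

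*Combined protocol and SAP*

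**What the plan says.** The outcomes are ranked in two places. Under Objectives, the primary objective is "To examine the effect of music-based occupational therapy on attention performance in children with ADHD" and the secondary objective is "To evaluate the effects of the intervention on executive function skills and caregiver burden". Under Outcome Measures, the primary heading holds one item, beginning "Change in attention (DSM-V Level 2 Inattention Scale". The secondary heading holds the executive-function inventory and the caregiver-burden scale. All measures are taken before and after the intervention.

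Two other places speak more loosely. The Background and Rationale says: "This study investigates the effect of music-based occupational therapy on attention and executive functions in children with ADHD". The description of the experimental arm under Intervention speaks of "sessions designed to improve self-regulation and executive functions".

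The Data Analysis Plan lists the chi-square test, the t-test or Mann-Whitney U test, and a two-way repeated-measures ANOVA for time interactions within and between groups. It ends with a common threshold: "The significance level for all tests was accepted as" p < 0.05. It gives no outcome by name, no designated confirmatory test, and no statement that the secondaries are supportive.

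**The concern.** Read alone, the analysis section puts every test on the same footing. The background sentence joins attention and executive function without ranking them, and the intervention text names executive function but not attention. Executive function could then seem to have two standings: secondary in the formal lists, and equal partner in the narrative.

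What would be at stake is the reading of a split result. If executive function reached p < 0.05 and attention did not, an author relying on the background sentence could say that the study met its aim, while the stated primary objective would not support that. Two secondaries tested at 0.05 each also give more than a 5% chance that at least one is falsely significant.

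**Working it through.** **1. The texts side by side.**
- The Objectives and Outcome Measures sections agree with each other: one primary (attention) and two secondaries (executive function, caregiver burden).
- The background sentence comes before the Objectives and describes the subject of the study. It omits caregiver burden, which is a formal secondary outcome, so it cannot be a list of outcomes or a decision rule.
- The intervention text describes what the sessions contain. It names self-regulation, which is not an outcome at all, so it says nothing about the rank of endpoints.

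Neither loose sentence contradicts the labels.

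**2. Inputs for the arithmetic.** The only figure in the plan is the per-test level of 0.05, so there is no stated error rate to reproduce. Assumptions: one between-arm test per outcome, no true differences, and normal test statistics with correlation r. The documents give no r, so the range 0 to 0.9 is shown. The critical value is c = 1.96.

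**3. Formulas.**
- (A) At least one of two tests significant, two-sided: 1 − P(|Z₁| ≤ c, |Z₂| ≤ c). At r = 0: 1 − 0.95² = 0.0975.
- (B) At least one significant in favour of music therapy: 1 − P(Z₁ ≤ c, Z₂ ≤ c). At r = 0: 1 − 0.975² = 0.0494.
- (C) Executive function significant and attention not, two-sided: (A) − 0.05. At r = 0: 0.0975 − 0.05 = 0.0475.
- (D) As (C), with executive function favouring music therapy: half of (C), by symmetry.

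| r | A | B | C | D |
|---|---|---|---|---|
| 0 | 9.75% | 4.94% | 4.75% | 2.4% |
| 0.3 | 9.51% | 4.76% | 4.51% | 2.3% |
| 0.5 | 9.07% | 4.54% | 4.07% | 2.0% |
| 0.7 | 8.35% | 4.17% | 3.35% | 1.7% |
| 0.9 | 7.04% | 3.52% | 2.04% | 1.0% |

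A t-test simulation with an assumed 20 children per arm and 200,000 trials per value of r gave 9.7/9.5/9.0/8.4/7.1% for (A). The primary alone came out at 4.9% to 5.1%.

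**4. Which figure fits the concern.** (A) and (B) describe the pair of secondaries. Labelled secondaries need no familywise control when they are read as supportive, so (A) measures something that calls for no correction. The split result is (C) and (D), and both stay below the nominal 5% for a single test.

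**5. What added wording would do.** Suppose the plan said that the secondaries are supportive and are reported with unadjusted 95% confidence intervals. An interval based on the same test excludes zero exactly when p < 0.05, so (A) would still be 9.75% at r = 0. Only a split level would lower it: with 0.025 each and r = 0, 1 − 0.975² = 4.94%. That correction is not needed here.

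**6. Which test decides the primary.** The primary outcome is a change, and the expected benefit is stated against standard therapy. Of the ANOVA effects, only the group-by-time interaction compares change between arms. With one measurement before and one after, its F statistic is the square of the two-sample t statistic on the change scores, so these two routes give the same p-value.

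**The case for a change.** The strongest case for a change concerns the primary test itself. The analysis section lists several tests and does not say which answers the primary objective. Both arms receive therapy, so improvement within the music arm alone would not show an advantage over control. The Expected Outcomes section lists benefit on all three outcomes without ranking them. The trial is open label, which is a further reason to settle the reading in writing. A sentence or two would do it, with no effect on data collection or on primary power.

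Part of this stands. The plan does not write down the deciding contrast, and the 5% error of the primary holds only if a single test decides it. A t-test or Mann-Whitney test on post-intervention scores would be a different test from the interaction. If subscales or the ANOVA main effects were also read as evidence of efficacy, the figures for the secondaries would be lower bounds; the documents do not say whether they will be.

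It does not show a defect that needs repair. The labelled primary is a change, and the planned ANOVA includes the interaction that compares change between arms, so the sensible reading is available without new text. Restating the ranking would be tidy drafting, but its absence does not undo the labels. A rule that the secondaries show no benefit unless the primary is significant would work as a gate, implying that they could be confirmatory once it is passed. That would raise a multiplicity question the present plan does not have. The analysis section is also written in the past tense. If results were already known, new wording could not count as pre-specification.

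**Conclusion.** The concern does not call for a change. The plan names one primary outcome and two secondaries, consistently, in both places where rank is set. The background and intervention sentences do not alter that ranking. The primary's error is 5% provided that one test decides it, and the group-by-time comparison of change is the natural candidate.

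The 7.0% to 9.8% chance of at least one false-positive secondary (3.5% to 4.9% in favour of music therapy) is correct under the assumptions of one test per outcome, no true differences and correlation from 0.9 down to 0. It describes ordinary unadjusted secondaries, and clearer wording would leave it as it is. The split result at issue has a probability of 2.0% to 4.8%, or 1.0% to 2.4% in favour of music therapy. The remaining gap is missing detail that an analyst fills sensibly: attention decides the trial, and executive function and caregiver burden support it.

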## **Ethical Considerations**

Approved by Istanbul Medipol University Non-Interventional Clinical Research Ethics Committee (E-10840098-772.02-2028).

All caregivers provided informed consent prior to participation.

### **Expected Outcomes**

Music-based occupational therapy is expected to improve selective attention, executive function, and reduce caregiver burden compared to standard therapy.

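### Does expecting better selective attention commit the trial to an effect that no listed outcome measures?

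*Combined protocol and SAP*

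**What the plan says.** The combined protocol and SAP describes attention in four places.

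- Background and Rationale: "This study investigates the effect of music-based occupational therapy on attention and executive functions in children with ADHD".
- Primary Objective: "To examine the effect of music-based occupational therapy on attention performance in children with ADHD".
- Primary Outcome: "Change in attention (DSM-V Level 2 Inattention Scale", the only attention measure listed.
- Expected Outcomes: "Music-based occupational therapy is expected to improve selective attention, executive function, and reduce caregiver burden compared to standard therapy".

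The two other expected effects follow a consistent line. The Secondary Objective reads "To evaluate the effects of the intervention on executive function skills and caregiver burden", and Secondary Outcomes lists "Executive Function (Childhood Executive Function Inventory" and "Caregiver Burden (Zarit Burden Scale", each with its instrument in brackets. All three measures are taken before and after the intervention.

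The Data Analysis Plan names tests (t-test or Mann-Whitney U, chi-square, two-way repeated-measures ANOVA) and a 0.05 significance level. It names no attention variable beyond the listed outcome and does not refer to the Expected Outcomes section.

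**The concern.** Selective attention is a narrower term than attention. A reader who checks the list of expected effects against the list of outcomes finds a partner for executive function and for caregiver burden, but none of that name for the first item. Because that item corresponds to the primary objective, the plan seems to predict one thing and measure another where it matters most.

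What would be at stake is the conclusion, not the estimate. If the report took its wording from Expected Outcomes, a difference between groups in inattention score would be presented as evidence about a particular kind of attention, and the plan states no basis for that step. The primary objective's phrase, attention performance, is also looser than a scale score, which adds to the impression that the attention construct has not been fixed.

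**Working it through.** There is nothing to calculate. The point depends on no sample size, effect size, standard deviation or power, and the plan gives no such figure. The check is a side-by-side reading.

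| Expected effect | Objective | Listed outcome | Same name? |
|---|---|---|---|
| Selective attention | Primary: attention performance | Primary: attention, by the DSM-V Level 2 Inattention Scale | No |
| Executive function | Secondary: executive function skills | Secondary: Childhood Executive Function Inventory | Yes |
| Caregiver burden | Secondary: caregiver burden | Secondary: Zarit Burden Scale | Yes |

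**Step 1: is the mismatch real?** Yes, as a matter of names. Two of three effects match and one does not. The word *selective* occurs once in the text available, in Expected Outcomes.

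**Step 2: is an attention outcome missing?** No. Attention in the broad sense is the primary outcome. The first row differs only in how specific the label is.

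**Step 3: is the primary objective left undefined?** Not in practice. The Primary Outcome supplies the instrument and says that change is the quantity of interest, the outcomes section gives the two assessment times, and Study Design gives the two groups. Together these say that attention performance is judged by change in the inattention score, music-based against standard occupational therapy. A definition added to the objective would repeat them.

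**Step 4: does the adjective alter anything done?** Take it as loose wording for attention: the analysis compares the two groups on change in the inattention score. Take it literally: no other attention measure is listed, so the analysis is the same comparison. Data, tests and estimate do not depend on the reading.

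**Step 5: does the plan show that the scale cannot speak to selective attention?** No. It describes none of the scale's items or subscales. What can be said from the document is that no basis is stated for a claim about selective attention. Whether the scale captures any part of it cannot be settled either way from this text.

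**Step 6: would editing now help?** The Data Analysis Plan is in the past tense ("The analyses were performed using SPSS 25.0 software"), so the analyses may already be complete. In that case, rewording an expectation afterwards adds little. What counts is that the report names the measure, and the Primary Outcome already does so.

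**The case for a change.** The best case for a change is this. Expected Outcomes is the only place where the plan gives a direction of effect and a comparator in the same sentence, so it serves as the hypothesis. The primary construct then carries three labels (attention performance, attention measured by an inattention scale, selective attention), the last narrower than the others. Aligning them would cost a few words and could only make the claim more careful. If the adjective was loose, nothing is lost by dropping it; if it was literal, the trial lists no measure described as capturing it.

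Part of this stands. The labels do differ, and a conclusion about selective attention would have no stated support in the plan.

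The step to a required change does not stand. The sentence is an expectation; it defines no outcome, sets no decision rule and specifies no test. The sections that do define what is studied and measured agree with one another. The harm depends on a future author copying one adjective in preference to the named primary outcome, and nothing in the plan says that conclusions will be worded from Expected Outcomes. That an edit would be cheap does not make it needed when it alters no procedure and no result.

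**Conclusion.** No change to the plan is called for. This is a clerical inconsistency of one word, found in 1 of 3 expected effects, with no consequence for the participants enrolled, the data collected, the analysis or the estimate. An analyst following the document compares the groups on change in the DSM-V Level 2 Inattention Scale and reports a result about that score, which is a sound conclusion.

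This rests on two assumptions. The first is that the report words its primary conclusion from the Primary Outcome, as is ordinary practice. The second is that no further attention measure exists outside the document. If a published conclusion did claim an effect on selective attention, the objection would lie against that report, which would need to justify the term. The trial's design and analysis would not be at fault.
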